latent infections in subjects who received single doses of elenbecestat. A single dose of elenbecestat up to 800 mg is not considered to pose clinical safety concerns with regard to immune function.

In the MAD study, AEs of interest included relapse of orolabial herpes, viral respiratory tract infection, drug rash, and abnormal dreams. More details are available in the Investigator's Brochure. In summary, elenbecestat administered at doses of 200 and 400 mg was associated with reductions in CD4 (T helper cells), CD8 (cytotoxic T cells), and CD19 (B cells) counts at Day 8. These reductions were more clearly evident by Day 15, consistent with a treatment by time interaction in the statistical analysis. There was evidence that the lower doses of 50 to 100 mg also caused some reduction in CD4 lymphocyte counts by Day 15. Doses above 100 mg appeared to be associated with greater reductions in CD4 and CD8 lymphocyte counts, which occurred earlier in the treatment period compared with the effects of 25 to 100 mg doses. These effects on lymphocyte counts gradually resolved from Day 20 to Day 35, which were 6 and 21 days, respectively, after administration of the last dose of elenbecestat on Day 14. Reductions in CD4 and CD8 lymphocyte counts at doses of 200 and 400 mg to a level close to or less than the lower limit of normal (LLN) could be associated with increased risk of developing relapse of orolabial herpes or other infections.

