9.3.3 Removal of Subjects from Therapy or Assessment

The investigator may withdraw the subject from the study at any time for safety or administrative reasons. The subject may stop study drug or withdraw from the study at any time for any reason.

Absolute lymphocyte count from the hematology and differential panel will be monitored during the study. Absolute lymphocyte count will be derived from the CBC with differential representing the normal lymphocytes (with atypical lymphocytes removed and presented as a separate count if they are present) and calculated by the white blood cell count \times percentage of lymphocytes. Should a subject develop a Grade 2 or greater lymphocytopenia (less than $800/\text{mm}^3$), the ALC test should be repeated as soon as possible with the repeat blood sample drawn no later than 5 calendar days from the date of the original test result. If confirmed, study drug administration should be interrupted for a minimum period of 2 weeks and for a maximum period of 4 weeks. Restart of study drug may take place only when ALC returns to greater than $800/\text{mm}^3$. Absolute lymphocyte count will be measured 4 weeks after restart of study drug. Subsequent measurements of ALC will follow the schedule of assessments (Table 5) and any results showing a Grade 2 or greater lymphocytopenia (less than $800/\text{mm}^3$) should be handled as above. If a Grade 2 or greater lymphocytopenia (less than $800/\text{mm}^3$), that is confirmed on repeat testing occurs twice within a 6-month period during the Core Study, then the subject should be discontinued permanently from the study drug. In the Extension Phase, if a confirmed Grade 2 or greater lymphocytopenia (less than $800/\text{mm}^3$) occurs twice from Visit 16 onwards during a 6-month period then the subject should be discontinued permanently from study drug. (revised per Amendments 01, 02, 04, and 06)

Subjects who develop moderate or severe hepatic impairment (eg, Child-Pugh Class B or C) during the study must discontinue study drug. (revised per Amendments 02 and 03) Moderate or severe hepatic impairment are defined as any 2 of the following criteria: INR ≥ 1.7 ; bilirubin $\geq 1.5 \times \text{ULN}$; albumin $< \text{LLN}$; ascites or hepatic encephalopathy. Please note that a single significant abnormality could meet criteria for moderate impairment. (revised per Amendment 03)

Subjects who develop seizures will be discontinued from study drug. (revised per Amendment 03)

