All subjects in the Core Study who discontinue study drug before reaching 12 months of treatment will also be asked to return to the clinic for a 12-month clinical assessment and then again at 24 months. Subjects who discontinue treatment between 12 and 24 months of treatment will be asked to return to the clinic for a 24-month clinical assessment. Subjects who discontinue early from study drug are considered “on study” as long as they continue to return for their regularly scheduled clinical assessments at 12 and 24 months as outlined above, at which efficacy and quality of life will be assessed along with concomitant medications. New AEs will be collected for 4 weeks post last dose and followed up for 12 weeks, or until resolution, whichever comes first. AEs relating to study procedures will be collected until the end of study participation. (revised per Amendment 06) However, subjects who discontinue study drug early are not considered to have ‘completed’ the study as a final Subject Disposition.

The primary reason for discontinuation and all other reason(s) contributing to the subject’s discontinuation from study drug(s) should be collected on the ED from study drug eCRF page. In addition, the date of last dose of study drug(s) will be recorded on the Study Drug Dosing eCRF page. If a subject discontinues study treatment and the study at the same time, the end-of-study procedures (Final Visit) will be followed (see [Section 9.5.5](#)).

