9.5.1.5.1 ADVERSE EVENTS AND EVENTS ASSOCIATED WITH SPECIAL SITUATIONS

An AE is any untoward medical occurrence in a subject or clinical investigation subject administered an investigational product. An AE does not necessarily have a causal relationship with the medicinal product. For this study, the study drug is elenbecestat.

The criteria for identifying AEs in this study are:

- Any unfavorable and unintended sign (including an abnormal laboratory finding), symptom, or disease temporally associated with the use of an investigational product, whether or not considered related to the investigational product (Note: Every sign or symptom should not be listed as a separate AE if the applicable disease [diagnosis] is being reported as an AE)
- Any new disease or exacerbation of an existing disease
- Any deterioration in nonprotocol-required measurements of a laboratory value or other clinical test (eg, ECG or x-ray) that results in symptoms, a change in treatment, or discontinuation of study drug
- Recurrence of an intermittent medical condition (eg, headache) not present pretreatment (Baseline)
- An abnormal laboratory test result should be considered an AE if the identified laboratory abnormality leads to any type of intervention, withdrawal of study drug, or withholding of study drug, whether prescribed in the protocol or not.

All AEs observed during the study will be reported on the eCRF. All AEs, regardless of relationship to study drug or procedure, should be collected beginning from the time the subject signs the study ICF until 4 weeks post last dose, and followed up for 12 weeks, or until resolution, whichever comes first (as shown in [Table 5](#)). Adverse events relating to study procedures will be collected until the end of study participation. Subjects who fail screening primarily due to AE(s) must have the AE(s) leading to screen failure reported on the Screening Disposition eCRF and the Adverse Event eCRF. (revised per Amendment 06)

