The following AEs will require the collection of information sufficient to provide a detailed description of the event, treatment, and outcome to the medical monitor for the study: any treatment-emergent significant laboratory abnormality; any seizures, herpes zoster infection, severe infection (eg, sepsis; deep tissue (invasive) infection; any infection requiring IV antibiotics; any infection requiring hospitalization (if outpatient at onset); any infection leading to need for oxygen, pressors or fluids to support blood pressure, or intubation; any infection that requires major surgical intervention; pseudomembranous colitis due to *C. difficile*; typhlitis; osteomyelitis; and meningitis); any moderate to severe drug rash or any rash lasting more than 72 hours (regardless of severity); treatment-emergent depigmentation/hypopigmentation/vitiligo/loss of hair color; amyloid-related imaging abnormalities (cerebral vasogenic edema, macrohemorrhage, an area of superficial siderosis, or a new microhemorrhage); a positive suicidality assessment on either the C-SSRS or the clinical assessment of suicidality. (revised per Amendments 03 and 06)

All AEs must be followed for 12 weeks after the subject's last dose, or until resolution, whichever comes first. Subjects who have a Grade 2 or greater lymphocytopenia (less than $800/\text{mm}^3$) during the Follow-up Period (ie, at either Visit 14 or Visit 15) should have ALC measured every 4 weeks until resolution or confirmation of a non drug-related cause of the lymphocytopenia; ALC will be derived from the CBC with differential representing the normal lymphocytes (with atypical lymphocytes removed and presented as a separate count if they are present) and calculated by the white blood cell count \times percentage of lymphocytes. (revised per Amendments 01 and 02) All SAEs must be followed to resolution or, if resolution is unlikely, to stabilization.

Every effort must be made by the investigator to categorize each AE according to its severity and its relationship to the study treatment.

Assessing Severity of AEs

AEs will be graded on a 3-point scale (mild, moderate, severe) and reported in the detail indicated on the eCRF. The definitions are as follows:

Mild Discomfort noticed, but no disruption of normal daily activity

Moderate Discomfort sufficient to reduce or affect normal daily activity

Severe Incapacitating, with inability to work or to perform normal daily activity

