reported during the first 4 weeks following the last dose of study drug that might indicate physical dependency also require a more detailed follow-up through completion of the same eCRF form. Categories and examples of AEs indicating signals of possible drug abuse are provided in [Appendix 3](#) and a more comprehensive list is provided in the eCRF Completion Guidelines. (revised per Amendments 02 and 04)

- bb: The first dose of study drug will be given to the subject at the study site. Subjects will be encouraged to stay at the site for observation for at least 30 minutes following their first dose of study drug. The duration of this observation period can be extended at the investigator’s discretion, eg, if warranted by medical history or concomitant medication. (revised per Amendment 04) Visit 2 bottles are re-dispensed at Visit 3 after accountability is performed. (revised per Amendment 06)
- cc: Only for Extension Phase subjects who did not participate in optional longitudinal substudies in the Core Study but who wish to consent to optional longitudinal substudies in the Extension Phase
- dd: For subjects entering the Extension Phase only
- ee: Immunological assessments only required for subjects randomized before 07 Sep 2018
- ff: New AEs will be collected for 4 weeks post last dose and followed-up for 12 weeks, or until resolution, whichever comes first. If >4 weeks post last dose, AEs relating to study procedures will be collected only
- gg: C-SSRS to be completed if any positive responses from the Clinical Assessment of Suicidal Thinking and Behavior
- hh: For those subjects entering the Extension Phase, NPI-12 will be used if available and both NPI-10 and NPI-12 scores calculated.
- ii: Not required for those entering Extension Phase

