9.5.4.1 Reporting of Serious Adverse Events

All SAEs, regardless of their relationship to study treatment, must be reported on a completed SAE form by email or fax as soon as possible but no later than 24 hours from when the investigator becomes aware of the event.

SAEs, regardless of causality assessment, must be collected up to 4 weeks after the last dose of study drug. All SAEs must be followed to resolution or, if resolution is unlikely, to stabilization. Any SAE judged by the investigator to be related to the study treatment or any protocol-required procedure should be reported to the sponsor regardless of the length of time that has passed since study completion. (revised per Amendment 06)

The detailed contact information for reporting of SAEs is provided in the Investigator Study File.

For urgent safety issues, please ensure all appropriate medical care is administered to the subject and contact the appropriate study team member listed in the Investigator Study File.

It is very important that the SAE report form be filled out as completely as possible at the time of the initial report. This includes the investigator's assessment of causality.

Any follow-up information received on SAEs should be forwarded within 1 business day of its receipt. If the follow-up information changes the investigator's assessment of causality, this should also be noted on the follow-up SAE form.

Preliminary SAE reports should be followed as soon as possible by detailed descriptions including copies of hospital case reports, autopsy reports, and other documents requested by the sponsor.

The investigator must notify his/her IRB/IEC of the occurrence of the SAE in writing, if required by their institution. A copy of this communication must be forwarded to the sponsor, or its designee, to be filed in the sponsor's Trial Master File.

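### New AEs and any-cause SAEs are collected for only 4 weeks after the last dose, although safety follow-up runs to Week 12 and lymphocytopenia is tracked beyond it

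*Protocol*

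**What the plan says.** The 4-week limit appears in several places of the current protocol (Version 8.0).

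- Section 9.3.3: "New AEs will be collected for 4 weeks post last dose and followed up for 12 weeks, or until resolution, whichever comes first".
- Section 9.5.1.5.1 collects all AEs, whatever their relationship to drug, from consent "until 4 weeks post last dose, and followed up for 12 weeks, or until resolution, whichever comes first".
- Table 5, note ff: "If >4 weeks post last dose, AEs relating to study procedures will be collected only". Note b says the same for early discontinuers.
- Section 9.5.4.1: "SAEs, regardless of causality assessment, must be collected up to 4 weeks after the last dose of study drug". The same paragraph adds an exception with no time limit: "Any SAE judged by the investigator to be related to the study treatment or any protocol-required procedure should be reported to the sponsor".

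The safety follow-up lasts longer. Section 9.1.2.2 schedules Visit 14 at 4 weeks and Visit 15 at 12 weeks after the last dose for all subjects, and Sections 9.3.3 and 9.5.5 give safety monitoring as one purpose of these visits. Table 5 marks both hematology and adverse events at Visit 15. Under Section 9.5.1.5.1 (repeated in Table 5, note c), subjects with Grade 2 or greater lymphocytopenia at Visit 14 or 15 "should have ALC measured every 4 weeks until resolution or confirmation of a non drug-related cause of the lymphocytopenia".

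Three other sections bear on the point. Section 9.4.7 has the investigator enter on the AE form the event for which a concomitant medication was given. Section 9.7.1.5 records medications throughout the 12-week Follow-up Period. Section 9.5.5 includes AEs among the assessments when early discontinuers return at 12 and 24 months.

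**The concern.** The protocol keeps measuring a laboratory marker off drug but stops recording the clinical events that the marker is meant to warn of. Section 7.1 gives the reason for watching lymphocytes: in the multiple ascending dose study, reductions at the two highest doses "could be associated with increased risk of developing relapse of orolabial herpes or other infections". A subject found lymphopenic at Visit 14 or 15 has the count repeated every 4 weeks. If that subject then develops a nonserious infection, or a serious one judged unrelated, the AE rule does not collect it.

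The gap is the same in both arms, so it does not by itself favor either. What is lost is the comparison: for onsets after Week 4 there is no complete count in either arm. Related SAEs reported at any time do not replace it, because each has already passed through an individual causality judgment.

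The sections also give a site conflicting instructions on whether to enter a late event. Sites that resolve the conflict differently will ascertain late events unevenly.

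**Working it through.** **Length of the gap.** Inputs are the study days in Table 5 (Visit 13, Day 729; Visit 14, Day 757; Visit 15, Day 813), taking Visit 13 as the end of dosing.

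- Visit 14: 757 − 729 = 28 days = 4 weeks. Visit 15: 813 − 729 = 84 days = 12 weeks. Both match Section 9.1.2.2.
- Days without collection of new non-procedural AEs: 84 − 28 = 56 days = 8 weeks; 56/84 = 67%.

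**Subjects with lymphocytopenia off drug.**

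- Table 5, note a, allows ±3 days, so Visit 14 falls on days 25 to 31. A subject found lymphopenic there has at most 28 − 25 = 3 days of new-AE collection left. One first found at Visit 15 has none.
- For a confirmed low count during treatment, Section 9.3.3 says "study drug administration should be interrupted for a minimum period of 2 weeks and for a maximum period of 4 weeks". The same section drops the 1-month Follow-up Visit if a suspended subject goes on to stop permanently 3 weeks or more after the last dose. At that early discontinuation visit at most 28 − 21 = 7 days of collection remain, and the next scheduled follow-up visit is Visit 15.

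**Conflicts in the text.**

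- *Medication against AE rule.* An anti-infective started in Week 8 off drug is recorded (Section 9.7.1.5). Section 9.4.7 then asks for the event behind it on the AE form. Table 5, note ff, excludes that event unless it is procedure-related.
- *Section 9.5.5 against Section 9.3.3 and Table 5, note b.* A subject who stops at Visit 7 (26 weeks after first dose) and returns at Visit 9 (52 weeks) is 52 − 26 = 26 weeks off drug. Section 9.5.5 has AEs assessed at that visit. The other two texts leave only procedure-related events to collect as new.

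**Size.**

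- Unobserved time, all elenbecestat subjects pooled over both studies (950, Section 9.7.2): 950 × 56/365.25 = 146 subject-years. If 70% reach Visit 15: 665 × 56/365.25 = 102.
- Events in lymphopenic subjects. The protocol gives no off-drug rates, so these are assumptions: 0.5% to 5% of 950 subjects lymphopenic throughout the 8 weeks, and 0.2 to 1.0 infections per subject-year.
  - Low end: 950 × 0.005 × 56/365.25 × 0.2 = 0.15 per arm.
  - High end: 950 × 0.05 × 56/365.25 × 1.0 = 7.3 per arm.
  - Any of these that are serious and judged related would still be reportable.

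**The case against.** The strongest reply is that a 4-week window is a deliberate choice, set by Amendment 06 and repeated consistently in the main AE and SAE text. Following a known abnormality after closing the window for new events is not in itself contradictory; the protocol treats open AEs the same way. Section 7.1 gives the window some support: lymphocyte counts recovered between 6 and 21 days after the last dose, inside 4 weeks. The infection-risk sentence concerns 200 and 400 mg, whereas this trial gives 50 mg, and for 50 to 100 mg only some CD4 reduction is reported. These points stand as limits on the concern. They do not settle it, because the recovery data follow 14 days of dosing rather than 24 months, and the sponsor still scheduled hematology at Week 12 with open-ended repeat counts.

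A reader might infer more than the text supports:

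- *That all infections after Week 4 go unrecorded.* Related SAEs are reportable without time limit, and infections that began earlier are followed to Week 12, or to resolution or stabilization if serious.
- *That the repeat counts show a drug effect.* The rule covers any Grade 2 or greater count and ends once a non-drug cause is confirmed.
- *That a subject whose count has not recovered after a 4-week interruption must stop permanently.* For lymphocytopenia, Section 9.3.3 states permanent discontinuation only for two confirmed episodes within 6 months.
- *That 146 subject-years measures the harm.* It covers all elenbecestat subjects, not those with low counts.
- *That former placebo subjects will have late events misclassified as treatment-emergent in the Extension Phase.* Entrants are examined at Visit 15, and an event present before the first Extension dose meets the definition only if it re-emerges or worsens, or if its onset is misdated.

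**Conclusion.** The concern holds in limited form. New AEs, and SAEs of any cause, are collected for one third of the safety follow-up the protocol itself schedules; the remaining 56 of 84 days capture only procedure-related AEs and SAEs judged related. Nonserious infections and serious infections judged unrelated that start in Weeks 5 to 12 are not available by arm, including in subjects with documented lymphocytopenia. The conflicts with Sections 9.4.7, 9.7.1.5 and 9.5.5 stand on the text alone and need no clinical assumption.

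The clinical yield is uncertain. The protocol neither shows nor excludes a lymphocyte effect lasting beyond 4 weeks after 24 months of dosing, and it gives no off-drug event rates. Under the assumed ranges the missed infections in lymphopenic subjects run from well under one to about seven per arm. This is a worthwhile, inexpensive improvement in safety ascertainment. It does not touch the efficacy analysis.

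**What to change.** Reconcile the AE and SAE collection text in Sections 9.3.3, 9.5.1.5.1, 9.5.4.1 and 9.5.5 and in Table 5, notes b and ff, with the Visit 15 safety assessment, the lymphocyte follow-up in Section 9.5.1.5.1 and Table 5, note c, and the medication recording in Sections 9.4.7 and 9.7.1.5. The reconciled text should have new AEs recorded over the follow-up already scheduled, that is, through Visit 15. It should also say what is recorded while repeat lymphocyte counts continue after Visit 15, and which AEs are collected when early discontinuers return at 12 and 24 months.

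Summarize onsets after Week 4 by arm in a separate post-treatment table. The TEAE definition in Section 9.7.1.8.2 has a start but no end, so without this late events would be mixed with on-treatment ones.

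The cost is amendment wording and slightly more data entry at a visit already scheduled for every subject, where the AE row is already marked. Some unrelated late events will be recorded; the separate table contains them. No dose, interruption or stopping rule changes.

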9.4 Treatment(s)

9.4.1 Treatment(s) Administered

Core Study

For this study, the test drug is elenbecestat and the control drug is placebo. All study drug is to be administered orally, once daily (QD), in the morning with or without food. As shown in [Figure 1](#), there will be 2 treatment arms where the elenbecestat arm will be administered a single dose of 50 mg per day and the control arm will be administered placebo.

Study treatment will begin on Day 1 (at the study site) following randomization and will continue for approximately 24 months. Please refer to [Table 5](#) and [Section 9.5.1.4.1](#) for specific information regarding study drug administration on days when PK sampling is to be performed.

Study drug dose will remain the same for each individual subject throughout the duration of the study. If a subject develops a concurrent illness during the Treatment Period, the investigator should discuss with the medical monitor whether dosing with study drug needs to be temporarily suspended. As a general clinical guideline, dosing with study drug may be resumed after resolution or stabilization of the concurrent illness, after discussion with the medical monitor.

Rules for discontinuing study treatment for subjects due to skin rash or to severe infections are described in [Section 9.5.1.5.5](#).

For details on treatment to be administered in the Extension Phase, refer to [Appendix 5 in Section 12](#).

